4.3.2 Incarcerated Participants

Participants who become incarcerated during the course of the study may have to be withdrawn; continued collection of data from incarcerated subjects would be on a case-by-case basis after consultation with the IRB.

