6.4 Study procedures – HCV treatment

During HCV treatment and in the follow-up period, patients with HCV will undergo monitoring for treatment adherence and safety per Standard of Care. Laboratory parameters and imaging used as part of the study endpoints are listed below. See Appendix B Study Schedule.

Cholesterol measurements

Patients' total cholesterol and LDL cholesterol will be obtained at screening and week 72 for cardiac risk calculations.

Cardiac biomarker and systemic inflammation assessment

For all participants, labs will be drawn at screening, week 24, and week 72: high sensitivity CRP (hSCRP), high sensitivity TRP (hsTRP), soluble markers of inflammation (IFN- γ , TNF- α , IL-6, CXCL9, CXCL10, CXCL11) and activated and exhausted naïve and memory T cells (percent of CD8+ and CD4+ T-cells which are HLA-DR+, CD38+, Tim-3+, or PD-1+).

Cardiac MRI

A subset of patients will undergo cardiac MRI; up to 12 patients will be recruited from each of the three groups to undergo cardiac MRI at the NIH clinical center at Day -7 (interim visit) and week 72. Patients who are claustrophobic or cannot tolerate the MRI procedure will not be selected for this portion of the study. Cardiac MRI will be utilized to assess changes in myocardial injury, degree of post-contrast enhancement, T1 mapping, and the function of the myocardium. See Appendix C for more details.

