13.1 Sample Size Justification and Power

The proposal primary outcome for cardiovascular risk is change in hsCRP. The primary hypothesis is that HCV eradication will result in at least a two-fold decrease from the baseline elevated hsCRP to 12 months post-functional cure in HCV-monoinfected and HIV/HCV-coinfected patients, respectively. Based on a previous study, mean hsCRP before starting IFN-therapy in HCV-monoinfected patients was 0.97 ± 0.11 mg/L compared to 0.07 ± 0.07 mg/L in healthy controls(23). Among SVR patients the median hsCRP at baseline was 0.64 mg/L and decreased to 0.25 mg/L after treatment. With a sample size of 30 patients in each group, we assume than 95% will achieve SVR with Zepatier (elbasvir/grazoprevir), resulting in a sample size of 28 patients in each group. In a paired t-test analysis (from baseline to 12-month post-treatment), with $\alpha=0.05$, power of 90% ($1-\beta$), and standard deviation (σ) = 0.15, we will be able to detect a true difference in the mean hsCRP response of matched pairs of 0.1 mg/L in each group or 0.8 mg/L with 80% power.

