13.2 Statistical Analysis

We will perform univariate analysis to describe the demographic and clinical characteristics of the study population. Count with percentages will be calculated for categorical variables and mean + standard deviation or median (interquartile range) for continuous variables. The independent variable is the three groups of participants with HCV, HIV/HCV, and HIV. Separate analysis will be done for each study group for the change in the primary outcome of HsCRP, from baseline to 18 months after baseline, in a paired t-test analysis, as well as for the secondary outcomes of cardiac biomarkers, MRI, and cellular and soluble immune markers of activation. Baseline comparison of hsCRP, cardio biomarkers, MRI, and cellular and soluble immune markers of activation between the three groups of participants will be performed using one-way or Kruskal-Wallis analysis of variance (ANOVA) for continuous variables and chi-square test of independence or Fisher's exact test for categorical variables. A linear regression model will be used in adjusted analysis for continuous dependent variables, while logistic regression model will be used in adjusted analysis for binary dependent variables. All analysis will be conducted in SAS, version 9.4 (SAS Institute, Inc., Cary, NC) with a P-value of less than 0.05 indicating statistical significance.

14 Ethics/Protection of Human Subjects

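### Week-24 hsCRP is collected in every group but assigned to no analysis, and the primary paired t-test drops anyone without a week-72 sample; a three-visit model of log hsCRP would use it

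*Combined protocol and SAP*

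**What the plan says.** Section 13.1 sets the endpoint: "The proposal primary outcome for cardiovascular risk is change in hsCRP". On sampling, section 6.4 states: "For all participants, labs will be drawn at screening, week 24, and week 72". It introduces these measurements with "Laboratory parameters and imaging used as part of the study endpoints are listed below", and Appendix B shows the same three time points for both HCV groups and the HIV mono-infected group.

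Section 13.2 analyses change "from baseline to 18 months after baseline, in a paired t-test analysis", separately in each group, and compares the groups at baseline. It adds that "A linear regression model will be used in adjusted analysis for continuous dependent variables", without naming a time point, covariates or a repeated-measures structure. No sentence gives the week-24 values a role, and there is no missing-data method or sensitivity analysis.

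On losses, section 13.1 reduces 30 per group to 28 for failure to reach SVR and for nothing else. Section 4.3.2 says "Participants who become incarcerated during the course of the study may have to be withdrawn". Section 10 ends follow-up on withdrawal but lets data already collected be used, and section 10.1 bars return.

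**The concern.** A paired t-test needs both values. Over 72 weeks some participants will probably give the first two samples and miss the third. The plan drops them from the primary analysis, although section 10 would allow their data to be used and their week-24 value says something about the missing one.

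Two things are at stake. One is precision, in groups of about 28. The other is bias: if those with higher hsCRP at week 24 are more likely to leave, the completers are a favourable selection and, on the log scale, their average fall is too large. That error favours the study hypothesis. Leaving the week-24 data without a stated role also leaves their later use to choice.

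**Working it through.** **1. The plan's own figure.** Inputs from section 13.1: n = 28, "standard deviation (σ) = 0.15" (taken as the SD of the paired difference), alpha 0.05 (two-sided assumed). The noncentral t distribution gives a detectable difference of 0.095 mg/L at 90% power, which agrees with the stated 0.1 after rounding. Power at 0.1 mg/L is 92.5%. (At 80% power the result is 0.082, so the printed 0.8 mg/L does not reproduce; that is a separate point.)

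The figure presumes a week-72 sample from every cured patient. With assumed loss at week 72:

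| Loss | Pairs | Power for 0.1 mg/L | Detectable at 90% power |
|---|---|---|---|
| 0% | 28 | 92.5% | 0.095 mg/L |
| 10% | 25 | 89.2% | 0.101 mg/L |
| 20% | 22 | 84.6% | 0.109 mg/L |
| 30% | 19 | 78.5% | 0.118 mg/L |

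**2. Precision recovered by the third visit, loss at random.** Assumptions, none from the documents: ln hsCRP with SD 1 at each visit; correlation 0.5 between screening and each later visit; correlation r = 0.7 or 0.8 between weeks 24 and 72; week 24 observed in everyone.

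- Variance of an individual's change: 2(1 - 0.5) = 1.
- Share of the week-72 variance explained by the two earlier visits: R² = (0.25 + r² - 2 × 0.5 × 0.5 × r)/(1 - 0.25). For r = 0.7: (0.25 + 0.49 - 0.35)/0.75 = 0.52. For r = 0.8: (0.25 + 0.64 - 0.40)/0.75 = 0.653.
- With loss d and n_c = 28(1 - d) completers, the ratio of model variance to paired variance is R²(1 - d) + (1 - R²)[1 + 2d/(n_c - 4)]. The last term is the small-sample cost of estimating the regression.

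| Loss | r = 0.7 | r = 0.8 |
|---|---|---|
| 20% (n_c = 22.4) | 0.416 + 0.480 × 1.022 = 0.906 | 0.523 + 0.347 × 1.022 = 0.877 |
| 30% (n_c = 19.6) | 0.364 + 0.480 × 1.038 = 0.862 | 0.457 + 0.347 × 1.038 = 0.817 |

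Simulation gives reductions of about 9%-13% and 14%-17%, in line with this. In pairs, at 20% loss the model is worth 22.4/0.906 = 24.7 to 22.4/0.877 = 25.5, so it recovers 2 to 3 of the 5.6 lost. At 0% loss the ratio is 1: same estimate, same standard error.

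**3. Bias when drop-out depends on week 24.** Assume the log-odds of missing week 72 rise by 1 per SD of week-24 ln hsCRP. The bias of the paired estimate is (r - 0.5) × E[week-24 z-score among completers]. Integrating over the normal distribution gives that mean as -0.173 at 20% loss and -0.253 at 30%.

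| Loss | r = 0.7 | r = 0.8 | SE of paired estimate |
|---|---|---|---|
| 20% | 0.2 × -0.173 = -0.035 | 0.3 × -0.173 = -0.052 | 1/√22.4 = 0.211 |
| 30% | 0.2 × -0.253 = -0.051 | 0.3 × -0.253 = -0.076 | 1/√19.6 = 0.226 |

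The fall is overstated by up to a quarter of a standard error at 20% loss (0.052/0.211) and a third at 30% (0.076/0.226). Against the hypothesised two-fold fall (ln 2 = 0.693) that is 5%-7.5% and 7%-11%. The model's bias is near zero. If all three correlations are equal, the factor r - 0.5 becomes zero and the paired test is not biased by this mechanism.

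**4. Scale.** Repeating step 3 on raw skewed values (exponentials of the same ln values, halved after baseline, true change -0.824 with the baseline median scaled to 1) reverses the sign. The paired test understates the fall by 0.023 to 0.067, the model is off by 0.015 to 0.032, and the model's root mean squared error is worse (about 0.40-0.44 against 0.37-0.39). The gain therefore depends on modelling log hsCRP.

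**5. Drop-out that depends on the unseen week-72 value.** On the plan's mg/L scale with SD 0.15, 20%-30% loss and between-visit correlations of 0.5 to 0.8, the paired test is biased by -0.013 to -0.025 mg/L and the model by -0.013 to -0.035. The model does not cure this case.

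**The case against.** The best case for the plan is that this is a pilot using a conventional test that matches its power calculation, and that the documents state neither a drop-out rate nor a direction. Section 6 says only that people who miss visits will be contacted, and section 4.3.2 treats incarceration case by case. Retention is supported: people unable to comply with visits are excluded (section 4.3), those who stop treatment early may stay in follow-up (section 6.5), and visits are paid (section 11). If nearly everyone reaches week 72, nothing is gained. All of this stands; it limits the size of the point but does not remove it.

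Several stronger readings are tempting and are not supported:

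- A reader might infer that the model protects against informative drop-out in general. It does so only when drop-out depends on observed values (step 5).
- A reader might infer that the week-24 data will never be used. Section 13.2 assigns them to no analysis, but its adjusted regression names no time point, so later use is not excluded.
- A reader might infer that the planned estimate is seriously biased. Even under the assumed mechanism, the bias is at most about a third of a standard error.
- A reader might want every participant with any hsCRP value in the model. The primary objective and section 13.1 concern change after functional cure, so adding patients without SVR would change the question.

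**Conclusion.** The point holds as a modest, inexpensive improvement to the primary analysis. Section 13.2 leaves the week-24 markers without a role, and its paired t-test removes anyone lacking a week-72 sample, with no missing-data method. A three-visit likelihood model of log hsCRP loses nothing with complete data. Under the stated assumptions it lowers the variance of the week-72 change by about 9%-13% at 20% random loss and 14%-17% at 30%. It also removes a log-scale bias of about 0.03-0.05 or 0.05-0.08 ln units if drop-out rises with week-24 hsCRP. The existence of the gap is certain from the text. The size is conditional, because the documents give no drop-out rate, correlation or log-scale SD. The gain also requires a week-24 sample from those who later miss week 72; someone lost before week 24 adds little.

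**What to change.** In section 13.2, for each HCV group separately:

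1. Define the primary population as participants with functional cure (SVR), as in the primary objective and section 13.1, and state which HCV RNA assessment decides membership.
2. Make the primary analysis a likelihood-based repeated-measures model of log hsCRP: visit as a factor (screening, week 24, week 72), unstructured covariance, Kenward-Roger degrees of freedom. The week 72 minus screening contrast, back-transformed to a fold change, is the primary estimate and speaks directly to the two-fold hypothesis.
3. Keep the paired t-test on log hsCRP in complete pairs as a sensitivity analysis.
4. State that the model assumes drop-out depends only on observed values. Add a sensitivity analysis for dependence on the unseen week-72 value, for example imputing missing week-72 log values with a range of upward shifts.
5. Use the same model for the other markers measured at all three visits, log-transformed where skewed.

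The cost is a few lines of plan text and SAS code, some extra analysis work, reliance on a stated missing-data assumption, and a restatement of section 13.1 on the log scale. No new patients, visits or samples are needed.

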14.1 Informed Consent Process

Informed consent is a process where information is presented to enable persons to voluntarily decide whether or not to participate as a research subject. It is an on-going conversation between the human research subject and the researchers, which begins before consent is given and continues until the end of the subject's involvement in the research. Discussions about the research will provide essential information about the study and include: purpose, duration, procedures, alternatives, risks and benefits. Subjects will be given the opportunity to ask questions and have them answered.

The subjects will personally sign and date the informed consent document prior to undergoing any research procedures. The subjects may withdraw consent at any time throughout the course of the trial. A copy of the informed consent document will be given to the subjects for their records. Consenting process will be documented in the record. The rights and welfare of the subjects will be protected by emphasizing to them that the quality of their medical care will not be adversely affected if they decline to participate in this study.

Per NIH policy, subjects participating in the MRI portion of the study will be consented with a NIH consent for the cardiac MRI that takes into account that the NIH is subject to the Privacy Act and is therefore not a HIPAA covered institution.

14.2 Illiteracy and Consenting

As the majority of the patient populations from which the study participants are drawn are literate, written consent will be obtained. Per UMB IRB policy, for participants unable to read, the written informed consent and any other written information will be read and explained to the participant by the person obtaining consent. An impartial third party will be present for the entire consent process. Once the subject has orally consented, the participant and witness will sign the consent form.

14.3 Subject Confidentiality

All records will be kept confidential to the extent provided by federal, state and local law. The study monitors and other authorized representatives of the Sponsor may inspect all documents and records required to be maintained by the Investigator, including but not limited to, medical records. Records will be kept locked and all computer entry and networking programs will be done with coded numbers only. Clinical information will not be released without written permission of the subject, except as necessary for monitoring by IRB, FDA, the Joint Commission or the HHRP.

APPENDIX B: Study Procedures Table

					M6	M18
HCV Treatment	Screening	Interim visit (Day -7)	Day 0	End of Treatment	Week 24	Week 72
Provider Visit	X^		X	X	X	
HCV SOC Labwork	X			X	X	
HCV RNA	X			X	X	X
HCV Ab	X^					^
HIV 4 th gen Ag/Ab	X					
HIV SOC Labwork	^					
HBV DNA (for HBcAb positive)	X^					
Total Cholesterol and HDL Cholesterol	X^					X^
Fibroscan or Fibrosure	X^				X^	
hsCRP, hsTRP	X^				X^	X^
Markers of inflammation	X^				X^	X^
Memory T cells	X^				X^	X^
Cardiac MRI		X^				X^
Urine Drug Screen	X^					

X= HCV mono- and HIV/HCV co-infected

^= HIV mono-infected

APPENDIX C: Cardiac MRI

Introduction and MRI Procedure

Cardiovascular magnetic resonance imaging (MRI) is an excellent imaging modality capable of assessing cardiac anatomy, myocardial function, myocardial infarction/fibrosis, as well as many other types of myocardial diseases. Patients infected with the hepatitis C virus are at increased risk of cardiovascular disease. Cardiac MRI can be used to assess for epicardial coronary artery plaque, sequela of epicardial coronary artery disease, such as myocardial infarction, as well as microvascular disease.

Each patient participating in the MRI scan will receive an oral and written explanation of the purposes, procedures, and risks of this study in language appropriate for the individual's level of understanding.

All cardiac MRI scans for this study will be performed on an FDA approved 3.0T or 1.5T scanner (Aera - Siemens Healthcare, Erlangen, Germany). The radiofrequency power levels (SAR limits) will be kept within the FDA established limits. A body coil will be used during the exam. A body coil is a noninvasive device external to the body that acts as antennae to receive radiofrequency signals out of the body. The body coil used during the MRI exam will follow FDA parameters.

For the cardiovascular MRI exam, patients will receive an intravenous injection of gadolinium chelate (Gadavist, 0.15 mmol/kg) via an MRI compatible power injector.

Inclusion Criteria for the Cardiovascular MRI

18 years of age or older

Written informed consent

Exclusion Criteria for the Cardiovascular MRI

Patients with the following devices are excluded from participating in the cardiovascular MRI study:

- Central nervous system aneurysm clip
- Implanted neural stimulator
- Implanted cardiac pacemaker or defibrillator
- Cochlear implant
- Ocular foreign body (e.g. metal shavings)
- Implanted insulin pump
- Metal shrapnel or bullet

The following groups of people are excluded:

- Pregnant women
- Lactating women unless they are willing to discard breast milk for 24 hours after receiving gadolinium
- Patients with stable renal disease (estimated glomerular filtration rate (eGFR) < 30ml/min/1.73 m² body surface area). The eGFR must be within 2 weeks of the MRI exam. Patients who are over 60 years of age, have a history of renal failure, or have type I or II diabetes mellitus must have laboratories the same day as the MRI exam.

- Patients with acute renal disease.

Monitoring Patients during the Cardiovascular MRI scan

The cardiovascular MRI exam is expected to last 60 to 90 minutes in duration. The MRI technologist will monitor the exam. Monitoring includes continuous ECG-gating. Blood pressure and pulse oximetry will be measured if clinically indicated. Patients may elect to withdraw from the MRI scan at any point.

Benefits/Risks of the Cardiovascular MRI

The cardiovascular MRI exam with gadolinium contrast involves greater than minimal risk, however may be of direct benefit to the individual patients [45 CFR 46.102(i)]. A clinical report of the exam will be available for the patients' physician.

MRI does not use ionizing radiation, and is extremely safe on a properly screened population. There is potential risk related to the magnetic field strength in patients with implanted metal devices (cochlear implants, etc), resulting in movement of these objects and subsequent harm to the patients. Patients will be screened for these objects (see exclusion criteria above) and excluded if they meet any of the exclusion criteria.

Peripheral nerve stimulation is unlikely to occur with our imaging parameters. It occurs when the magnetic field gradient switch occurs so fast that it results in peripheral nerve depolarization. The patient may feel a twitch or possibly some pain. Patient education as well as audio feedback from the patient during the exam will be used for the issue of possible peripheral nerve stimulation.

The scanner is operated within FDA guidelines for radiofrequency power levels. However, there is a small chance that a damaged or dysfunctional coil could cause some local warming in the body. Thus, for safety purposes, we ask all patients to report this sensation so we can modify scans and also verify the integrity of the hardware.

Gadolinium Administration for the Cardiovascular MRI exam

Patients must have an IV placed for gadolinium administration. Potential risks of IV placement include discomfort, bruising/bleeding, and vasovagal reactions.

The gadolinium agent used for the cardiovascular MRI exam, Gadavist, is commercially available and routinely used in hospital radiology practices. Studies in large patient populations have shown that gadolinium is safe without side effects in the majority of patients. If side effects occur, they are often mild and include headache and nausea. Severe reaction such as shortness of breath, wheezing, and hypotension are rare. The US Food and Drug Administration has issued a warning that the administration of gadolinium (updated September 9, 2010) has been associated with development of a disease call nephrogenic systemic fibrosis (NSF). All cases to date have occurred in patients with severe renal disease, including patients on dialysis. NSF has been nearly eradicated by avoiding gadolinium contrast use in patients with creatinine clearance <30cc/min.⁴⁻⁷

On July 27, 2015, the US Food and Drug Administration issued a safety announcement stating that they are investigating the risk of brain deposits of gadolinium contrast agents. Several studies have shown a correlation between high signal intensity

in the dentate nucleus and globus pallidus of the brain on unenhanced T1-weighted images and the number of previous administrations of gadolinium contrast agents in both adult and pediatric patients with normal renal function, suggesting deposition of the gadolinium contrast agent into the brain.

More recently, autopsy studies have confirmed that gadolinium deposits in the brains of patients with normal renal function as well as in other organs including the bones and the skin. Murata et al showed that macrocyclic gadolinium contrast agents deposit in the body to a significantly lesser degree than the linear open chain gadolinium contrast agents. The effects (adverse or otherwise) of gadolinium deposition in patients with normal renal function remains unclear and the FDA investigation is ongoing.

The gadolinium agent used for our cardiovascular MRI exams is Gadavist, which is a macrocyclic type of gadolinium contrast based agent. Macrocylic agents are currently considered the safest type of gadolinium based contrast agent available.

References

